1.12. DATA MANAGEMENT

The researcher and assistants allocated the patient a study serial number. No identifiers were used.

1.13. DATA CLEANING AND ENTRY

Completed questionnaires were checked for validity, accuracy and completeness by the principal investigator before data entry into the computer by the research assistant

1.14. OUTCOMES

1.14.1. Primary Outcome

1. Incidence of PPH defined by blood loss equal to or exceeding 1,000 ml following elective caesarean section

- Based on calculated estimates.

1.14.2. Secondary Outcomes

1. Incidence of PPH defined by blood loss equal to or exceeding 1000 ml following elective caesarean section

- Based on visual estimation

2. Estimated blood loss during caesarean section

- Based on visual estimate of blood loss and calculated estimates

3. Need for blood transfusion

- Mean or median number of units of red blood cells transfused up to day 2 postpartum

4. Use of additional uterotonicics (such as oxytocin infusion or prostaglandins)

- Number of participants who required additional uterotronics

5. Incidence of emergency surgical interventions for PPH up to day 2 post-surgery

6. Mean change in HCT up to day 2 post-surgery

- Difference between the HCT on the day before surgery and day 2 post-surgery

7. Mean peripartum change in haemoglobin up to day 2 post-surgery

- Difference between the haemoglobin on the day before surgery and at day 2 post-delivery

8. Duration of mother's hospital stay

9. TXA side effects

- number of participants with headache, anaphylaxis, nausea, diarrhoea, dizziness, fatigue, nasal sinus complaints, transient visual disturbances, abdominal pain, complaints of feeling faint, reported by anaesthetists and theatre staff [time frame: up to discharge from the recovery ward on day of surgery]
- number of participants with deep venous thrombosis, pulmonary embolism, myocardial infarction, or any thrombotic event confirmed by laboratory investigations up to day 2 post-surgery
- number of participants with seizures up to day 2 post-surgery
- number of participants with renal failure (defined by the need for dialysis) up to day 2 post-surgery
- number of participants with hypotension reported by anaesthetists and theatre staff [time frame: up to discharge from the recovery ward on day of surgery]
- Vital signs before surgery
 - Heart rate before surgery
 - Systolic BP before surgery
 - Diastolic BP before surgery

- Vital signs after placental delivery
 - Heart rate after delivery of the placenta
 - Systolic BP after delivery of the placenta
 - Diastolic BP after delivery of the placenta
- Post-caesarean delivery creatinine (mg/dL)
- Postoperative urea g/L
- Postoperative aspartate transaminase (IU/L)
- Postoperative alanine transaminase (IU/L)
- Postoperative total bilirubin (IU/L)

10. Neonatal outcomes

- Birth weight in grams determined on the date of delivery
- Apgar scores at 1 and 5 minutes on the date of delivery
- Reason for admission to NNU/NICU [time frame: up to discharge from NNU/NICU]
- Number of neonates with neonatal jaundice determined clinically [time frame: up to discharge from NNU/NICU]
- Number of neonates with thromboembolic events determined clinically [time frame: up to discharge from NNU/NICU]
- Number of neonates who died [time frame: up to the day of discharge of the mother]

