2.2.3. EVIDENCE ON USE OF TRANEXAMIC ACID IN OTHER SURGICAL CONTEXTS

Regardless of the type of surgery (cardiac, orthopaedic, hepatic, urological, and vascular), in a systematic review of RCTs including 20,781 participants, TXA was shown to reduce the risk of transfusion of blood by 39% [RR 0.61 (95% CI 0.54–0.69)], and the number of units transfused by 1.1 units (95% CI 0.64–1.59). The review also showed a statistically insignificant trend towards benefit on the need for re-laparotomy due to haemorrhage [RR 0.67 (95% CI 0.41–1.09)]⁽¹⁾.

A meta-analysis of 129 RCTs evaluating the impact of TXA in the prevention of bleeding at elective surgery of 10,488 participants showed a reduction of the need for a blood transfusion by 38% [RR 0.62(95%CI 0.58–0.65)]; regardless of the type of surgery⁽¹⁾.

The administration of TXA reduced mortality in bleeding trauma patients in high-, middle-, and low-income countries in the Clinical Randomisation of an Antifibrinolytic in Significant Haemorrhage (CRASH-2) trial⁽¹⁾.

Treatment with TXA has also been shown to reduce by 26 – 54% (a material reduction) bleeding in women with menorrhagia⁽¹⁾. This suggests that TXA can reduce bleeding from the uterus even in low amounts in a non-surgical scenario. The latter provides evidence to support the hypothesis that TXA is useful for the prevention of PPH after vaginal and caesarean births.

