1.11. STATISTICAL METHODS

Data analysis was conducted using Stata v15 (Stata Statistical Software: Release 15. College Station, TX: StataCorp LLC) following the CONSORT guidelines for reporting RCTs⁽⁵⁵⁾.

The primary analysis compared women given a low dose of TXA (10mg/kg) administered 10 minutes before elective caesarean section with prophylactic oxytocin administration to those given prophylactic oxytocin alone.

Baseline characteristics were compared between the groups to check the adequacy of randomization. Differences between patients lost to follow-up and included patients were also assessed. The intention-to-treat analysis was followed. This is a statistical concept whereby every participant in the study is accounted for in the analysis according to the randomization treatment assignment regardless of whether there is noncompliance, protocol deviations, withdrawal from the study, and anything happens after randomization⁽⁵⁶⁾.

Categorical data were reported using frequencies and proportions while continuous data were summarized using means and standard deviations for normally distributed data, and medians and quartile range where data was not normally distributed. Comparisons for categorical data were done using the chi-square test or Fisher's exact test when the sample size was small.

For continuous data, the t-test was used to compare differences between the groups and the analysis of variance (ANOVA) was used for comparing more than two groups. Where data were not normally distributed, the nonparametric Kruskal Wallis test was used to compare differences in continuous outcome for more than two groups. The Mann-Whitney U test was used to compare two groups where data were not normally distributed. Effect estimates were presented with relative risk measures and associated 95% confidence intervals. Any subgroup analysis was conducted as the primary analysis.

An analysis was conducted after 506 participants had been recruited to check if there are any significant differences in adverse events in the two groups.

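### Secondary outcome 3 is called need for transfusion but is measured only in red-cell units, so the planned summary will read 0 vs 0 with no usable effect estimate

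*Combined protocol and SAP*

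**What the plan says.** Section 1.14.2 (Secondary Outcomes) names item 3 "Need for blood transfusion" and gives it one measure: "Mean or median number of units of red blood cells transfused up to day 2 postpartum". The next item, additional uterotonics, is measured as "Number of participants who required additional uterotronics". Nothing in section 1.14 counts the women who received blood.

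Section 1.11 (Statistical Methods) follows intention to treat, with every randomised woman accounted for. Continuous data are summarised by "means and standard deviations for normally distributed data, and medians and quartile range where data was not normally distributed". For testing, "The Mann-Whitney U test was used to compare two groups where data were not normally distributed". On effect size it says: "Effect estimates were presented with relative risk measures and associated 95% confidence intervals".

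Section 2.2.3 treats transfusion as an event. One systematic review is reported thus: "TXA was shown to reduce the risk of transfusion of blood by 39"% (RR 0.61), with units transfused given separately (1.1 fewer). A meta-analysis of elective surgery "showed a reduction of the need for a blood transfusion by 38"% (RR 0.62).

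**The concern.** Whether a woman needs blood is a yes/no question, and a mean or median of units over all women does not answer it. If most women receive no blood, the units are mostly zeros with a short right tail. Such data are not normal, so the plan's own rule selects the median, and that median will be 0 in both arms. The wording also leaves the choice between mean and median open for this item, and the trial is open-label.

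What is at stake is the usefulness of one secondary outcome. Section 2.3 (Justification) gives lower use of blood products as one of the reasons for the trial. As planned, the trial would produce no proportion transfused and no relative risk for transfusion, so its result could not be placed beside RR 0.61 or 0.62.

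**Working it through.** **Inputs from the document.** PPH 2.1% and 5.8%, two-sided 5% level, 90% power, 581 per arm (Chapter 3, section 1.4, Sample Size); 506 recruited in the initial period (section 1.6, Randomization), or 506/2 = 253 per arm if split evenly; RR 0.61 for transfusion (section 2.2.3).

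**Inputs assumed.** The document gives no transfusion rate and no distribution of units. A range of rates is used. Units per transfused woman are taken as 1, 2, 3, 4, 6 and 10 with probabilities 0.30, 0.50, 0.10, 0.05, 0.03 and 0.02. This gives a mean of 2.18 and a mean square of 7.08.

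**1. The plan's own figure.** The only sample-size figure is for PPH. With the printed z-values, [1.96√(2 × 0.0395 × 0.9605) + 1.28√(0.021 × 0.979 + 0.058 × 0.942)]² / 0.037² = 579.8. With unrounded z-values it is 581, so the stated figure is reproduced. No figure is given for transfusion.

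**2. The median.** With 581 women the median is the 291st ordered value, so it exceeds 0 only if at least 291 are transfused. With 253 women the number is 127. The probability is P(X ≥ 291) or P(X ≥ 127) for X binomial(n, p):

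| Assumed rate p | 581 per arm | 253 per arm |
|---|---|---|
| 5.8% | 1e-194 | 4e-86 |
| 20% | 1e-58 | 1e-26 |
| 40% | 6e-7 | 0.0006 |
| 45% | 0.008 | 0.055 |

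The quartiles do not help: the upper quartile is also 0 unless about a quarter of the arm is transfused.

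**3. The mean.** Mean = 2.18p and variance = 7.08p − (2.18p)². At p = 1% the mean is 0.022 units with SD 0.265, a ratio of 12. At p = 10% it is 0.218 with SD 0.813, a ratio of about 4. If one further woman receives 10 units, her share of the arm's total is 10 / (2.18np + 10):

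| Assumed rate p | 581 per arm | 253 per arm |
|---|---|---|
| 1% | 44% | 64% |
| 2% | 28% | 48% |
| 5% | 14% | 27% |
| 10% | 7% | 15% |

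**4. Power by test.** Simulation, 581 per arm, 3,000 runs:

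| Control rate, RR | t-test on mean units | Mann-Whitney on units | Proportion transfused |
|---|---|---|---|
| 5%, 0.61 | 29% | 39% | 39% |
| 10%, 0.61 | 51% | 68% | 68% |
| 5.8%, 0.36 | 79% | 92% | 92% |

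Mann-Whitney matches the proportion test because nearly all the rank information lies in zero versus not zero. A heavier-tailed units distribution (mean 2.6) with 6% vs 2% transfused gives the same pattern at 253 per arm: t-test 49%, Mann-Whitney 64%, proportion 64%.

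**The case against.** Several points on the other side are sound.

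- **Power.** A reader might infer that measuring units costs the trial power. The document does not support this. Section 1.11 assigns non-normal two-group data to Mann-Whitney, which loses nothing against the proportion. The loss in step 4 occurs only if that rule is set aside for a t-test on the mean.
- **Rates.** It is tempting to read the PPH rates of 2.1% and 5.8% as transfusion rates. They are not: some women with PPH receive no blood, and some women are transfused for other reasons. The zero median survives this, since it needs only a rate clearly below one half. The dominance of the mean by a few women does not survive at every rate; it is strong at 1–2% and modest at 10%.
- **Units are legitimate.** Section 2.2.3 also cites a difference in units, and section 2.3 prices blood per unit. Units should therefore stay. What is missing is the proportion.
- **Relative risk.** The relative-risk sentence in section 1.11 is general and cannot apply to blood loss or length of stay either. It is not a contradiction specific to this outcome.
- **Denominator.** Item 3 does not state one. If only transfused women were summarised, the median would be at least 1. That would compare groups selected after randomisation and still would not measure need.

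What stands is that the planned summary gives a valid test with no interpretable size of effect.

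**Conclusion.** The point holds as a fault in the outcome's definition and reported summary. With all randomised women as the denominator, the planned result is a median of 0 vs 0 beside a p-value unless about half of an arm is transfused. No listed measure gives the proportion transfused or a relative risk. Reporting the mean instead would give an estimate that a few heavily transfused women can dominate when transfusion is rare, here assumed to be 1–2%.

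Nor should a reader infer that counting women makes this a well-powered comparison. At 581 per arm and RR 0.61, power for the proportion is 18%, 39% and 69% at assumed control rates of 2%, 5% and 10%. The gain is an interpretable estimate with a confidence interval. This is one of ten secondary outcomes, and the primary outcome and its sample size are unaffected.

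**What to change.** Under item 3 of section 1.14.2, add the number and proportion of women given any red-cell transfusion up to day 2, over all women randomised, as the measure of need. Report it with relative risk, risk difference and 95% CI. Keep units as description: total per arm, and their distribution among transfused women.

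No new data are needed, because transfused yes/no follows from the units that the existing measure requires. The cost is disclosure. The trial is open-label (section 1.7, Blinding), 506 women have been recruited, an analysis was run at that point (section 1.11), and the monitoring board has reviewed an analysis (section 3.16). The proportion should therefore be declared as a post hoc clarification of a secondary outcome and reported beside the listed units measure, not substituted for it without comment.

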2.4. RESEARCH OBJECTIVES

1. To determine the effect of TXA (10mg/kg) given intravenously 10 minutes prior to an elective caesarean section on postpartum blood loss.
2. To determine the potential adverse effects of intravenous TXA given 10 minutes prior to elective caesarean section.

CHAPTER 3. RESEARCH METHODS

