1.2. PARTICIPANTS

The participants were women undergoing elective caesarean sections at Harare and Parirenyatwa Hospitals.

Inclusion criteria

- Pregnant woman with signed informed consent***
- Understand English and/or Shona
- Estimated gestational age of 38 weeks or more
- Requiring Elective Caesarean Section defined as caesarean section performed before onset of labour
- Live intrauterine foetus

***The study enrolled participants who met the inclusion criteria including minors. Consent was sought from legally authorized representatives such as the parent or guardian where possible. Where this was not possible the pregnant participants who were under the age of 18 were considered emancipated minors by them having assumed adult responsibilities (becoming a mother) before 18 years of age ⁽⁵⁰⁾.

Exclusion criteria

Women with the following characteristics were excluded from the study:

- Placental Abruptio

- Emergency caesarean section
- Current or previous history of significant disease including heart disease, liver, renal disorders
- Known coagulopathy or history of deep venous thrombosis and/or pulmonary embolism, or arterial thrombosis (angina pectoris, myocardial infarction, stroke)
- History of epilepsy or seizures
- Autoimmune disease
- Sickle cell disease
- Intrauterine foetal demise
- Eclampsia/HELLP syndrome
- Administration of anticoagulants – clexane or antiplatelet agents in the week before delivery

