1.4. SAMPLE SIZE

The sample size was calculated assuming a proportion of 2.1% PPH in the experimental group and 5.8% in the control group ⁽³⁸⁾ at 95% confidence interval and 90% power using the Fleiss formula giving a minimum sample size of

$$\begin{aligned} n &= \frac{[Z_{\alpha/2}\sqrt{(r+1)\bar{p}\bar{q}} + Z_{\beta}\sqrt{rp_1q_1 + p_2q_2}]^2}{r(p_1 - p_2)^2} \\ &= \frac{[1.96\sqrt{(1+1) \times 0.0395 \times 0.9605} + 1.28\sqrt{0.021 \times 0.979 + 0.058 \times 0.942}]^2}{(0.021 - 0.058)^2} \\ &= 581 \text{ per group} \end{aligned}$$

Thus, total minimum sample size $N = 1,162$ women

Where: n = sample size

$Z\alpha = 1.96$ at 95% confidence interval

$\alpha = \text{probability of a type I error (significance level)} = 0.05$

$\beta = \text{probability of a type II error (1 - power of test)}$

$p_1 = \text{proportion of PPH in the experimental group} = 0.021$

$p_2 = \text{proportion of PPH in the control group} = 0.058$

$r = \text{ratio of control group/population 2 to experimental group/population 1}$

$q = 1-p$

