1.10. ASSESSMENT

Data were collected and recorded on the data collection tool. Any adverse event was to be reported on the MCAZ/MRCZ adverse event reporting form.

Vital signs (heart rate, blood pressure, respiratory rate) were recorded before surgery, immediately after placental delivery, and 1 to 2 hours after birth.

Full blood count (FBC), urea & electrolytes (U&E) and liver function tests (LFTs) were performed a day before delivery and on the second day after delivery.

Estimated blood loss (EBL) was determined using the difference in haematocrit values taken before and 48 hours after caesarean delivery according to the formula:

$$= \text{EBV} \times (\text{Preoperative haematocrit} - \text{Postoperative haematocrit})$$

Preoperative haematocrit

Where EBV (estimated blood volume) in ml is equal to the woman's weight in kg \times 85 ⁽³⁸⁾.

As haematocrit values were not consistently available, EBL was also determined using the haemoglobin (Hb) value using the Meunier's formula $BV \times [(Hb_i - Hb_e)/(Hb_e)]$, where BV is blood volume, Hb_i is initial Hb, and Hb_e is end Hb⁽⁵²⁾.

Standard EBL based on visual estimates made by anaesthetist after assessment of patient's linen and abdominal swabs was also recorded.

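### The maternal thrombosis outcome rests on an undefined laboratory confirmation whose scope is ambiguous and which, read literally, leaves out imaging and ECG

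*Combined protocol and SAP*

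**What the plan says.** All references are to the combined protocol and SAP.

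- **Outcome.** Section 1.14.2, item 9 (TXA side effects) has one line for maternal thrombosis: "number of participants with deep venous thrombosis, pulmonary embolism, myocardial infarction, or any thrombotic event confirmed by laboratory investigations up to day 2 post-surgery". Laboratory investigations are not defined there or elsewhere.
- **Scheduled tests.** Section 1.10: "Full blood count (FBC), urea & electrolytes (U&E) and liver function tests (LFTs) were performed a day before delivery and on the second day after delivery". No imaging, ECG or cardiac marker is mentioned anywhere as a way to confirm a thrombosis.
- **Adverse event route.** Section 1.10 also states: "Any adverse event was to be reported on the MCAZ/MRCZ adverse event reporting form". This carries no laboratory condition.
- **Contrast within the outcome list.** For the babies, section 1.14.2 counts "Number of neonates with thromboembolic events determined clinically", a different standard of ascertainment.
- **Stroke.** It is not named in item 9. The exclusion criteria (section 1.2) treat it as a form of "arterial thrombosis (angina pectoris, myocardial infarction, stroke".
- **Objective and analysis.** The second objective (section 2.4) is "To determine the potential adverse effects of intravenous TXA given 10 minutes prior to elective caesarean section". Section 1.11 adds: "An analysis was conducted after 506 participants had been recruited to check if there are any significant differences in adverse events in the two groups".
- **Blinding.** Section 1.7 says that participants and trial staff knew the allocation once the envelope was opened.

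**The concern.** DVT, PE and stroke are ordinarily confirmed by imaging, and MI by ECG together with a blood marker. A rule that asks for laboratory confirmation fits at most one of the events in the list. The laboratory tests that the plan does schedule are blood count, renal function and liver function, and none of these confirms a thrombosis.

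The grammar leaves open which events the condition governs, so two analysts who follow the text could report different counts from the same records. The outcome is rare, so one or two reclassified events could change what is said about it.

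At stake is a prespecified harm under the second objective. The plan takes this harm seriously elsewhere: the exclusions remove women with prior venous or arterial thrombosis, and section 2.2.4 faults a trial of 160 women for lacking power on thromboembolic complications.

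**Working it through.** **Step 1. The plan's own figure.** The plan states no rate or precision for thrombotic events. Its only relevant figure is the arm size from section 1.4, which was set for PPH "assuming a proportion of 2.1% PPH in the experimental group and 5.8% in the control group", with 90% power and two-sided alpha 0.05. The Fleiss formula without continuity correction and with unrounded normal quantiles gives 581 per group, as stated; the printed rounded values 1.96 and 1.28 give 579.8. The wording of the thrombosis outcome has no bearing on it. Below, n = 581 is the planned arm, and n = 253 is half of 506, which assumes an equal split.

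**Step 2. Apply the rule to constructed records under each parsing.**

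| Record by day 2 | Condition covers the whole list | Condition covers only the catch-all |
|---|---|---|
| DVT on ultrasound | not counted | counted, no criterion stated |
| PE on CT | not counted | counted, no criterion stated |
| MI on a blood marker | counted | counted, no criterion stated |
| MI on ECG alone | not counted | counted, no criterion stated |
| Stroke on CT | not counted | not counted |
| Other thrombosis on imaging | not counted | not counted |
| Suspected DVT, no test | not counted | can be counted |

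Neither column gives a count of objectively confirmed events. The stroke and other-thrombosis rows do not depend on the parsing.

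**Step 3. What a zero count would mean.** With zero events among n women, the exact two-sided 95% upper limit is 1 − 0.025^(1/n):

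- n = 581: 0.63%
- n = 253: 1.45%

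The one-sided 95% limits, 1 − 0.05^(1/n), are 0.51% and 1.18%. All of these presume that every true event would have been counted. In events, the two-sided limits are 0.0063 × 581 ≈ 3.7 and 0.0145 × 253 ≈ 3.7. An arm would therefore need at least 4 uncounted events before the limit was exceeded.

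**Step 4. How likely a zero is.** Let r be the true risk by day 2 and s the share of events that the rule captures. Both are assumptions. Then P(zero counted) = (1 − r·s)^n.

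| Assumed r | n = 581, s = 1 | n = 581, s = 0.5 | n = 253, s = 1 | n = 253, s = 0.5 |
|---|---|---|---|---|
| 0.1% | 56% | 75% | 78% | 88% |
| 0.2% | 31% | 56% | 60% | 78% |
| 0.5% | 5% | 23% | 28% | 53% |

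With s = 0 the probability is 100% throughout. Partial capture makes a zero more likely, but at 0.1% to 0.2% a zero is common even when nothing is missed.

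**Step 5. Effect on the comparison.** If the same share s is captured in both arms, the expected relative risk is (s·r1)/(s·r0) = r1/r0. It is unchanged, and the loss is in counts and precision. At r = 0.2%, the expected count in 581 women falls from 581 × 0.002 = 1.16 to 0.58 when s = 0.5.

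**The case against.** The best defence is that this is loose drafting. The condition directly follows the catch-all phrase and may govern only that; DVT and PE would then count however they were proven. Laboratory investigations may also have been meant broadly, as diagnostic tests in general. No passage says that an imaging result was or would be rejected. An event missing from this count is still reportable as an adverse event, the trial compared adverse events between arms at 506 women, and the safety board assesses safety data.

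Much of this stands. A reader might infer four stronger things that the documents do not support:

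- *That every imaging-proven event is excluded.* For DVT and PE this holds under one of the two parsings only.
- *That this is the main safety outcome.* It is one line among several under secondary outcome 9, and no safety outcome is ranked first.
- *That a reported zero would be false.* Step 4 shows that a true zero is plausible at either sample size.
- *That the rule hides an excess on TXA.* With equal capture in the two arms the expected relative risk is preserved; an excess is wholly hidden only if nothing is captured.

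The defence does not remove the defect. The narrow parsing leaves DVT, PE and MI without a criterion where staff know the arm, and it still puts stroke under the laboratory condition. Nothing says that the adverse event forms feed this count. The plan specifies ascertainment elsewhere, clinically for neonatal events and by need for dialysis for renal failure, so the choice of words here cannot simply be ignored.

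**Conclusion.** The point holds as a fault of definition. The confirmation criterion is undefined, its scope is ambiguous and, taken literally, it omits imaging and ECG. An imaging-proven stroke or other thrombosis fails it on either parsing; an imaging-proven DVT or PE fails it on one. The count could understate thrombotic events.

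The size of any undercount cannot be derived. The risks of 0.1% to 0.5% and the half-capture share are illustrations, and the limits of 0.63% and 1.45% describe the precision of a zero count, not evidence that events were lost. The conclusion rests on the literal sense of the wording and on the general fact that blood count, renal and liver tests do not confirm a thrombosis. It warrants correction because the repair is small and the outcome is a prespecified harm; it does not call the sample size or the primary analysis into question.

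**What to change.** Reword the line in item 9 to count participants with *DVT, PE, MI, stroke or any other thrombotic event, confirmed by imaging, ECG or laboratory investigation as appropriate to the event*, and keep the day 2 window. Then:

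1. Re-derive the count from existing notes and adverse event forms, by the same procedure in both arms.
2. List suspected but unconfirmed events separately by arm.
3. Report the new count beside the literal one and label it a post hoc clarification. The plan is written in the past tense, allocation was open, and adverse events have already been compared between arms.

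The cost is one sentence and a limited re-check of records, with no new tests, no new participants and no change to the sample size. The downside is that the count may be less favourable than the literal one, and that a definition settled after the data were seen carries less weight than one settled before.

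### The only count of women with renal harm is dialysis by day 2; the paired creatinine that the schedule provides is not used to count women with lesser injury

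*Combined protocol and SAP*

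**What the plan says.** Objective 2 (section 2.4) is to determine the potential adverse effects of TXA. Three parts of the plan bear on the kidney.

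- **Outcomes, section 1.14.2, item 9.** The one participant-level renal count is "number of participants with renal failure (defined by the need for dialysis) up to day 2 post-surgery". The same item also lists "Post-caesarean delivery creatinine (mg/dL") and "Postoperative urea g/L", both as post-operative levels, with no change from baseline and no threshold.
- **Assessment, section 1.10.** The schedule states that "urea & electrolytes (U&E) and liver function tests (LFTs) were performed a day before delivery and on the second day after delivery". The section also says: "Any adverse event was to be reported on the MCAZ/MRCZ adverse event reporting form".
- **Analysis, section 1.11.** "For continuous data, the t-test was used to compare differences between the groups", with Mann-Whitney where data are not normal. An analysis at 506 participants looks for differences in adverse events between the arms.

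Items 6 and 7 of section 1.14.2 define haematocrit and haemoglobin as differences between the day before surgery and day 2. Creatinine has no such definition. Women with "Current or previous history of significant disease including heart disease, liver, renal disorders" are excluded (section 1.2).

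**The concern.** Dialysis within two days of surgery is an extreme event in women selected to be free of significant renal disease. Take a woman whose creatinine goes from 0.6 to 1.8 mg/dL by day 2 without dialysis (an illustration, not a figure from the plan). She is not in the renal failure count. Her value enters a group comparison of post-operative levels, where a few such women are diluted among hundreds. The pre-operative value that would identify her as injured is scheduled but has no role in any outcome.

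What is at stake is how far the trial can inform objective 2 for the kidney. If the dialysis count is zero in both arms, the table could be taken as reassurance that the data cannot give. The renal outcome would also carry almost no information on injury short of dialysis.

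**Working it through.** **Sample size (section 1.4).** The documents give no renal event rate and no renal power figure. Their one sample size is for PPH: p1 = 0.021, p2 = 0.058, mean 0.0395, two-sided 5%, 90% power.

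n = [1.96√(2 × 0.0395 × 0.9605) + 1.2816√(0.021 × 0.979 + 0.058 × 0.942)]² / 0.037² = 580.4, rounded up to **581 per group**, as stated. With the printed 1.28 it is 579.8. The figure stands and is used below as the planned size. The other size is 506/2 = 253 per arm, from the number recruited in the initial period (section 1.6).

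Every renal rate, SD and noise figure below is an assumption, not a figure from the documents.

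**Step 1: the dialysis count.** P(no case in either arm) = (1 − p)^N.

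| Assumed dialysis risk p | N = 506 | N = 1,162 |
|---|---|---|
| 0.01% | 95% | 89% |
| 0.1% | 60% | 31% |

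If an arm has no case, the one-sided 95% upper bound for its risk is 1 − 0.05^(1/n): 1.2% at n = 253 and 0.5% at n = 581. That bound concerns dialysis only and says nothing about lesser injury.

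**Step 2: comparing mean post-operative creatinine.** Let 2% more TXA women have a rise of 0.5 mg/dL. The mean shifts by 0.02 × 0.5 = 0.01 mg/dL. Power ≈ Φ(0.01 / (SD√(2/n)) − 1.96).

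| Assumed SD (mg/dL) | n = 253 | n = 581 |
|---|---|---|
| 0.15 | 11% | 21% |
| 0.30 | 6% | 8% |

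**Step 3: a per-woman count.** Simulation: pre-operative creatinine N(0.6, 0.12), floored at 0.3 mg/dL; day-2 value = pre-operative value (doubled in injured women) + N(0, noise SD). The planned tests use the day-2 level. The count is women at or above 1.5 times their own baseline, compared by Fisher's exact test. All tests are two-sided at 5%, and every woman has both samples. Ranges span repeated runs with different seeds.

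| Per arm | Injured, TXA vs control | Noise SD | t-test | Mann-Whitney | Count |
|---|---|---|---|---|---|
| 581 | 2% vs 0% | 0.05 | 26–29% | 9–10% | 97–98% |
| 581 | 2% vs 0% | 0.10 | 23–26% | 10–11% | 74–79% |
| 581 | 2% vs 0% | 0.15 | 15–19% | 8–10% | 31–35% |
| 581 | 3% vs 0.5% | 0.05 | 37–38% | 10–12% | 89–91% |
| 581 | 2% vs 1% | 0.05 | 11% | 6% | 21–23% |
| 253 | 2% vs 0% | 0.05 | 13–15% | 6–7% | 37–41% |
| 253 | 2% vs 1% | 0.05 | 7% | 5% | 6–9% |

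At noise SD 0.15, about 3% of uninjured controls cross the 1.5-fold line by noise alone. If every woman also rises by 0.1 mg/dL after surgery (noise SD 0.10, 581 per arm, 2% vs 0%), about 4% of uninjured controls cross it, and the count has 27–30% power against 22% for the t-test.

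The count is ahead of both planned tests in every row but the last, where nothing has useful power. How far ahead depends heavily on the noise and on the control rate.

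**The case against.** **Other renal information is planned.** A reader might infer that kidney injury short of dialysis would go unreported. The documents do not support that. Creatinine and urea levels are listed side-effect outcomes, and any adverse event has a reporting form. This stands, and it limits the point to counts of women. It does not remove it: the comparison of levels is weak (step 2), and the documents give no creatinine criterion for the form, so capture would rest on individual judgement.

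**The pairs may be incomplete.** A reader might take creatinine as measured in every woman before surgery and on day 2. Section 1.10 gives a schedule, not a record of completion. It names U&E, so pre-operative creatinine is inferred, and it concedes of another scheduled test: "As haematocrit values were not consistently available". This stands. The simulations assume no missing pairs and are optimistic to that extent.

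**The advantage of the count is assumption-driven.** This also stands. The 97–98% figure needs little noise, no control events and a doubling in every injured woman. At 253 per arm even that favourable case gives only 37–41%.

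**A threshold added now is post hoc.** The plan is written in the past tense for an open-label trial, reports no design change after commencement (section 1.1 of the methods chapter), and says the DSMB has reviewed an analysis (section 3.16). The 1.5-fold and 2-fold lines are this review's choice and are not in the documents. The answer is to label the outcome plainly, not to leave it out.

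**Conclusion.** The point holds in limited form, as a cheap improvement to a secondary safety outcome. No planned outcome counts women with a creatinine rise from their own baseline, although the schedule provides for the pair and the plan treats haematocrit and haemoglobin that way. Under the assumptions above, the planned comparison of means has 6% to 21% power for a 0.5 mg/dL rise in 2% more TXA women. A per-woman count usually does better, but it would not make this an adequately powered renal safety study, least of all at 506 participants.

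Two stronger readings should be resisted. One is that the dialysis outcome is almost certain to be zero in both arms. The documents give no dialysis rate, and across assumed risks of 0.01% to 0.1% the chance of no case runs from 31% to 95%. The other is that the plan claims renal safety from a zero count. It makes no such claim; the risk is one of misreading. Nor is there a basis here for extending the proposal to liver enzymes: the documents state no multiple, and none was examined.

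**What to change.** Keep the dialysis count as defined. Add to item 9 of section 1.14.2, by arm:

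- the number of women whose day-2 creatinine is at least 1.5 times, and at least 2 times, their own pre-operative value;
- the number of women with both samples, as the denominator;
- a 95% confidence interval for the difference or ratio between arms.

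If outcome data have been seen, label this as added after the original outcome list. State in the report that zero dialysis cases is not evidence of renal safety, and give the upper confidence bound beside any zero.

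The cost is outcome and analysis wording, plus retrieval of pre-operative creatinine values where they exist; no new sampling is needed. The drawbacks are real: mild or noise-driven rises will be counted in both arms, women without both samples drop out, and precision will be low. Present the result as an estimate, not as a test.
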